### Procedures for providing follow up care:

Medical monitoring will occur at all clinic and follow up visits and medical care will be provided if warranted. If a study participant experiences any psychiatric symptoms or distress (e.g., depressive symptoms or

suicidality) at any stage of study participation he/she will receive short-term treatment and support from the study treatment team (including psychologists and a psychiatrist) and will be connected to a local emergency department (e.g., the Crisis Intervention Unit at Yale-New Haven Hospital) and his/her physician or therapist for ongoing care.

Measurement and reporting of subject accrual, adherence to inclusion/exclusion criteria.

Review of the rate of subject accrual and adherence to inclusion/exclusion criteria will occur regularly by the PI and co-Investigators and yearly by the DSMB. These reviews will help to assure that participants meet eligibility criteria and ethnic diversity goals outlined in the grant proposal.

Measurement and reporting of participant treatment completion rates.

Participation rates (retention and attrition) will be reviewed on an ongoing basis by the PIs and co-investigators to identify any potential problems, and formally by the PIs and DSMB semi-annually. Any differential dropout across blinded study groups and/or higher than expected dropout will be reviewed by the investigators to determine whether any problems are present and what, if any, corrective action needs to be taken.

During the reviews, if the DSMB has concerns about whether attrition has reached a level that might inhibit the ability of the study to address its primary aims, they will suggest a meeting to discuss methods for improving subject retention. Previous pharmacotherapy studies for BED (with comparable time frames for pharmacotherapy) have reported attrition rates between 20% and 38%. Studies of bupropion for obesity treatment reported attrition of 30% to 38%. Thus, "trigger points" for review and discussion by principal investigator and research staff will be: 35% ("low alert"), 40% ("mid alert"), 45% ("high alert"), 50% ("extreme alert"). With early alerts to problems, action would be taken to avoid higher level alerts; if a higher-level alert should arise, more drastic actions would be taken.

The following actions would be taken at each level of alert:

- (1) Low-level alert = Review of potential problems by PI.
- (2) Mid-level alert = Meeting with co-investigators to discuss approaches to minimize further losses to follow-up/dropouts.
- (3) High-level alert = Meeting with co-investigators to determine further alterations of study protocol to complete the study with no further losses.
- (4) Extreme-level alert = In the unlikely event of a 50% dropout rate prior to the mid-study time point, discontinuing the trial would be considered.

# **Trial Stopping Rules**

Given that this study is deemed greater than minimal risk to human subjects but not high risk, it is more likely that attrition or difficulty in recruiting adequate numbers of participants will require stopping the trial than would excess adverse events. However, as outlined, adverse events will be monitored in all participants, and the DSMB, together with the PI, will alert the Yale IRB and the NIH if a larger (or more serious) than

reasonably expected adverse event rate should occur. Other potential issues relating to stopping rules for this trial include:

### 1. New Information

It is unlikely that any new information will become available during this trial that would necessitate stopping the trial. If new safety data (i.e., pertaining to short-term use of the study medication) become available, this will be evaluated.

### 2. Limits of Assumptions

It is possible that baseline differences between the treatment conditions, excessive attrition, and/or missing data could limit the value of data analysis. Baseline differences across blinded treatment groups, if present, will be evaluated yearly and considered in relation to potential effects on the power to detect differences in the primary outcomes. If these effects were to develop and be sizeable, alterations to the randomization schedule would be considered. Any plans to alter the randomization scheme would be communicated to the NIH.

### 3. Limits of Rules

There are other situations that could occur that might warrant stopping the trial and/or including a section on the safety report entitled "Other situations that have occurred since the last safety report that warrant discussion" to allow for communication of concerns.

Finally, as currently outlined above, the DSMB has the authority to stop the trial following any serious adverse event or following any semi-annual review of adverse events.

### 13. **Statistical Considerations:** Describe the statistical analyses that support the study design.

Baseline demographic and clinical characteristics for the randomized groups will be compared using chi-square tests for categorical variables, and ANOVA or Kruskal-Wallis tests for continuous variables. Continuous variables will be examined for normality using normal probability plots and Kolmogorov-Smirnov test statistics. If normality is not satisfied, transformations or nonparametric alternatives will be considered. Dropouts and completers will also be compared. Primary analyses will be based on an intent-to-treat basis. Primary outcomes will be tested at the two-sided alpha 0.05 threshold. Secondary analyses will be adjusted for multiple tests using the Bonferroni correction basing the adjustment on the number of conceptually related statistical tests within each hypothesis.

Overall analysis strategy. Mixed-effects models [92] will be used to compare treatments. These models allow for different numbers of observations per subject, use all available data on each subject, and are unaffected by randomly missing data. A further advantage is the capacity to test and account for individual-difference contributions to the treatment outcomes (Cudeck, 1996; Cudeck & Klebe, 2002; Hedeker et al., 1996; Hedeker & Gibbons, 1996; Singer, 1998). They provide flexibility in modeling the correlation structure of the data. In models for each outcome in Aims 1 & 2, we will include obesity status (obese vs. non-obese) and treatment (NB vs. placebo) as between-subject effects, time (see Aim-specific study time points) as a within-subjects factor, and subject as the clustering factor. Across analysis, time-points associated with the 12-week treatment phase will be considered as primary outcomes, and all analyses will be repeated to examine change

during the 12-month follow-up period. All possible interactions will be modeled and the following primary a priori contrast will be tested: 1) placebo NB vs. active NB. Least-square means will be plotted and compared post-hoc to interpret significant effects. Because we cannot a priori predict the shape of the response over time in each arm of the trial we will first treat time as a categorical predictor and will then test for polynomial trends over time. We will consider different error structures (e.g., AR1, CS, independence) and select the best fitting one based on Schwartz' Bayesian Criterion (BIC). We will compare dropout patterns between groups and if there are concerns of informative dropout or informative intermittent missing data, we will use pattern mixture models [93] to perform sensitivity analyses. Secondary models will include subjects with complete data. To test for assessment reactivity, we will evaluate whether biosensor assessment (yes/no; between-subject variable) moderates our primary outcomes in Aim 1 (as either a main effect, or interacting with medication). If this is found, then all subsequent analyses for Aims 1 & 2 will be limited to the sample (n=140) without the biosensor assessment.

Primary Aim 1. We will use the mixed models described above to test the effectiveness of NB medication for BED patients with and without obesity. The primary aims are to evaluate NB medication for (a) reducing binge eating frequency; and (b) in the patients with obesity, for reducing % weight loss. Significant NB main effects (regardless of obesity status) on frequency of binge eating will be considered supportive of our primary hypothesis. We also expect that NB will be associated with significantly greater reductions in % weight loss among the BED+obese group. In view of the factorial design, we will also be able to assess whether obesity status moderates reductions in binge eating frequency. These analyses will focus on 12-week outcomes. Secondary analysis will be repeated to examine change during the 12-month FU period.

Secondary Aims. (a) Explore effectiveness of NB medication for BED patients with and without obesity on secondary outcomes: eating-disorder pathology (EDE global), eating behaviors (EDE, TFEQ, FCI, PFS), depression (BDI-II), psychosocial functioning (SF-36), metabolic measures (lipid profiles, HbA1c, blood pressure, heart rate) and "remission" and "relapse" from binge eating behaviors. The continuous secondary outcomes (e.g., EDE global, BDI-II, SF-36) will be analyzed using the same approach as for primary aim 1, and logistic regression will be used to compare proportion achieving remission from binge eating or relapse to binge eating. (b) Explore predictors, moderators, and mediators of primary outcomes (i.e., binge eating). In terms of treatment processes, we will attempt to replicate our findings regarding the prognostic significance of rapid response for behavioral and pharmacologic treatments ([name] et al., 2006, 2012, 2015; Masheb & [name], 2008). We will follow Kraemer's (2002) conceptual/statistical models for exploring predictors, moderators and mediators for binge eating. Per [name] et al. (2012), we hypothesize that overvaluation of shape/weight and depression levels to be significant predictors; such findings would inform future treatment prescription regarding this pharmacologic intervention. Per Kraemer (2002), we will explore if baseline characteristics predict/moderate treatment effects by testing for main effects and interactions in models specified above for primary outcomes. In terms of mediators, we will explore whether differential symptom changes during treatment are associated with subsequent longer-term primary outcomes. Repeated assessments of eating behaviors (EDEQ and TFEQ scales), and food-reward constructs (FCI, PFS) relevant to putative mechanisms of action for NB, will yield relevant change variables for analyses of mediation (i.e. testing subsequent changes in binge eating).

**Primary Aim 2**. To evaluate potential mechanisms underlying the effect of NB on binge eating behavior, we will first evaluate whether NB treatment changes latency to resist eating, calories consumed, leptin, ghrelin, and food craving employing the mixed models described above. If a potential mechanism demonstrates a significant time x medication effect, we will then evaluate whether improvement in the variable of interest mediates changes in frequency of binge eating over the 12-week treatment period. Following the general analytic framework outlined by Kraemer (2002), we will use the product of the coefficients method to

evaluate the relationship between the mediator, or indirect effect, and outcome. After running a regression equation to determine (1) the effect of treatment on the mediator (provides beta weight for a), we will evaluate (2) the strength of the relationship between the mediator, treatment, and outcome (provides beta b). Using MacKinnon's software PRODCLIN, we will evaluate the asymmetric confidence intervals for the product of the regression estimates (a\*b). Importantly, we note that statistical mediation is not equivalent to causation, and will be sure to appropriately limit our conclusions. Significant NB main effects in latency to resist eating, calories consumed, leptin, ghrelin, and food craving will be considered supportive of our hypothesis. Further, significant mediation of NB-related changes in lab variables on clinical outcomes (reduction in binge eating frequency) will be considered supportive of our hypothesis.

**Exploratory Aim 3**. To account for the hierarchical structure of the data, linear mixed models will be used to assess differences over time in affect and eating behaviors per day collected over a 6-week period. To evaluate potential mechanisms underlying triggers of binge eating behavior, we will first evaluate whether NB treatment changes eating behavior. We will also evaluate the time course of affect and eating behaviors to identify potential antecedents and consequences of binge eating episodes.

Supplementary analysis: Retention, compliance, and sex. These analyses will provide insight into outcomes which will help us to consider directions for future research. We plan to explore whether medication compliance [plasma bupropion, naltrexone, 6-beta-naltrexol levels, pill counts], and length of time in treatment influenced our primary outcomes. Analyses described earlier will be repeated separately with a) counts of pills taken as a covariate, and b) length of time in treatment as a covariate. In participants taking active medication we will conduct a logistic regression examining area under the curve for the three plasma medication levels as a predictor of our primary outcome (frequency of binge eating) and as predictor of treatment-related change in potential mechanisms. Associations between plamsa medication levels and changes in mechanisms will provide an indication that medication is driving the change in the predictor variable. We also plan to evaluate whether sex moderates medication effects on all study outcomes. Analyses described in D.7.3. will be repeated with sex as between subject variable. We will also explore effects related to laboratory outcomes assessing estrogen and progesterone levels as covariates.

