4. **Research Plan:** Summarize the study design and research procedures using non-technical language that can be readily understood by someone outside the discipline. **Be sure to distinguish between standard of care vs.** research procedures when applicable, and include any flowcharts of visits specifying their individual times and lengths. Describe the setting in which the research will take place.

Overview of Study Design

This single-site, proof-of-concept, clinical trial is a double-blind, placebo-controlled, parallel group study to test the effectiveness of naltrexone + bupropion (NB) pharmacotherapy in BED patients with and without obesity. BED patients with (BMI > 30 and <50) and without obesity (BMI >21.5 and <29.9), will be randomized to NB (32 mg/day naltrexone combined with 360 mg/day bupropion) or placebo (n=50 per cell, n=200 total).

Following eligibility screening and randomization, participants will start a 12-week medication treatment period, a treatment period consistent with other BED medication trials (McElroy et al., 2016). Participants will have four weeks of up-titration: one tablet daily (Naltrexone 8mg/ Bupropion 90mg; 1 week), then two tablets daily (Naltrexone 16mg/ Bupropion 180mg; 1 week), then three tablets daily (Naltrexone 24mg/ Bupropion 270mg; 1 week), to reach the full dose of four tablets daily (Naltrexone 32mg/ Bupropion 360mg). The dosage will continue for the remainder of the 3 months. Medication will be discontinued at the end of 3 months, and patients will then be followed 12-months post-treatment to assess the durability of medication effects. The primary outcome measure is reduction in binge-eating frequency.

To evaluate correlates and mechanisms of NB on eating behavior, assessments will occur in the laboratory and in the field to optimize internal and external validity. Participants will complete human laboratory sessions ("lab sessions") before the start of medication and then during the final week of the 12-week medication period to evaluate the ability to resist eating preferred high-caloric food and subsequent overeating. During the laboratory sessions, we will evaluate potential mechanisms including eating peptides

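### The plan does not settle whether Aim 1 has one primary outcome or two, and gives no test order or alpha split if it has two

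*Combined protocol and SAP*

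**What the plan says.** **Number of primary outcomes in Aim 1.** The Overview of Study Design (item 4) is unambiguous: "The primary outcome measure is reduction in binge-eating frequency". In Statistical Considerations (item 13), the Primary Aim 1 paragraph lists two: "The primary aims are to evaluate NB medication for (a) reducing binge eating frequency; and (b) in the patients with obesity, for reducing % weight loss". Hypothesis 1.2, on weight, also stands under Primary Aim 1 in the Statement of Purpose.

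Other sentences in item 13 point back to one outcome:
- The Primary Aim 1 paragraph ties a single primary hypothesis to binge eating: "Significant NB main effects (regardless of obesity status) on frequency of binge eating will be considered supportive of our primary hypothesis". Weight then enters as a further expectation.
- The Secondary Aims paragraph glosses the primary outcomes as binge eating.
- The Supplementary analysis paragraph identifies the primary outcome as binge-eating frequency.

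**Alpha.** Item 13 states: "Primary outcomes will be tested at the two-sided alpha 0.05 threshold". The next sentence is the only multiplicity rule: "Secondary analyses will be adjusted for multiple tests using the Bonferroni correction", counted over related tests within a hypothesis.

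**Aim 2.** The Primary Aim 2 paragraph says: "Significant NB main effects in latency to resist eating, calories consumed, leptin, ghrelin, and food craving will be considered supportive of our hypothesis". A measure with a significant treatment-by-time effect goes on to a mediation analysis. No alpha is given for these tests.

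**The concern.** The plan has to fix which result makes the trial positive before the treatment codes are opened. Here one reading gives a single test of binge eating at 0.05. Another gives two tests, each at the full 0.05, with success open on either. The choice between them could be made after the data are seen. Under the second reading the Aim 1 error rate is roughly double the stated threshold.

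The same kind of gap exists, with less consequence, for the laboratory measures. If they are primary, nothing corrects for testing five of them. If they are secondary, the Bonferroni rule applies, but the family is not defined. The plan does not say which.

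**Working it through.** The documents state no family-wise error rate and no power calculation, so there is no figure of the plan's own to reproduce.

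**Inputs from the documents**
- Two-sided alpha of 0.05 for primary outcomes (item 13).
- One Aim 1 primary outcome (Overview of Study Design) or two (Primary Aim 1 paragraph).
- 200 participants, of whom 100 have obesity (Statement of Purpose; Subject Population). The weight test therefore uses half the sample of the binge-eating test.
- Five laboratory measures (Primary Aim 2 paragraph): latency, calories, leptin, ghrelin, craving.

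**Assumed, because not given:** correlations between outcomes or tests of 0.3, 0.5 and 0.7. All null hypotheses are taken as true.

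**Aim 1, two tests at 0.05, either one counting**
- Independent: 1 − 0.95² = 0.0975. The bound under any dependence is 0.05 + 0.05 = 0.10.
- Correlated: with outcome correlation ρ, the test statistics correlate at ρ × √(100/200) = 0.707ρ. The error is 1 − P(|Z₁| < 1.96 and |Z₂| < 1.96) under a bivariate normal.

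| Outcome correlation (assumed) | Test correlation | Chance of at least one false positive |
|---|---|---|
| 0 | 0 | 9.75% |
| 0.3 | 0.212 | 9.6% |
| 0.5 | 0.354 | 9.4% |
| 0.7 | 0.495 | 9.1% |

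- Binge eating as the only primary outcome: 5%.
- Binge eating first, then weight only if binge eating is significant, each at 0.05: at most 5%. If binge eating has no true effect, any false positive requires that first test to err. If it has one, only the weight test can err.

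**Aim 2, five tests at 0.05, uncorrected**
- Independent: 1 − 0.95⁵ = 0.226.
- Equally correlated tests, by simulation: 20.9% at 0.3, 18.3% at 0.5, 14.9% at 0.7.
- Bonferroni over five: 0.05/5 = 0.01 each, giving 1 − 0.99⁵ = 4.9% if independent.
- If all five had to be significant: at most 5%.

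These Aim 2 figures are the chance that at least one measure falsely passes the gate to the mediation step. A mediation claim also needs the confidence interval for the product of the two coefficients, so its error rate is a different quantity and is not calculated here.

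**The case against.** The strongest reply on Aim 1 is that one primary outcome is the dominant reading. The Overview, the Secondary Aims paragraph, the Supplementary analysis paragraph and the stated success criterion all point to binge eating. Hypotheses 1.1 and 1.2 are also separate claims in different populations, in a single-site proof-of-concept trial, so joint error control is open to debate. Much of this stands: item 13 is not uniformly a two-outcome plan, and the 9–10% applies only if weight is also treated as primary. But the paragraph that defines the Aim 1 analysis does list weight among the primary aims, and no sentence ranks it below binge eating for testing.

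On Aim 2, a reader might infer that the plan tests each laboratory measure at 0.05 and exempts them all from Bonferroni. The heading of the aim suggests it, as does the sentence that treats 12-week time points as primary across analyses. Neither settles it. No sentence gives these measures an alpha or excludes them from the correction, and the 12-week sentence mainly separates treatment from follow-up.

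A reader might also infer that one significant measure out of five is enough to support the mechanism hypothesis. The success sentence joins the five with a plain conjunction and states no any-or-all rule. Nor are they clearly one family: Hypothesis 2.2 covers resisting food and calories consumed, while eating peptides and craving enter through the mediation hypothesis, 2.1.

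**Conclusion.** The inconsistency on Aim 1 is real and worth correcting. If both outcomes are primary and either can be claimed, the Aim 1 error is about 9–10% rather than 5%. That range holds across the assumed correlations because the two tests share only half the sample. If binge eating is the sole primary outcome, the error is 5% and only the wording is at fault.

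For Aim 2 the documents support a narrower conclusion: the alpha is unspecified. About 23% is the upper figure for five uncorrected tests under the normal model, falling to about 15–21% at assumed test correlations of 0.7 to 0.3. It concerns passing the gate to mediation, not a false mediation finding. It would be wrong to read it as the plan's stated error rate, or to pool both aims into one family, which the plan does not do.

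**What to change.** **Aim 1.** State in both the Overview and item 13 that binge-eating frequency is the single primary outcome, tested at two-sided 0.05. Test percentage weight change in the obesity stratum second, at two-sided 0.05, only if binge eating is significant.

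This follows the plan's own dominant wording and costs the binge-eating test no alpha. The downside is that weight is descriptive if binge eating fails. Splitting alpha at 0.025 each would keep a formal weight test in every case, with error 1 − 0.975² = 4.94% if independent. It would, however, raise the difference detectable with 80% power for binge eating from (1.960 + 0.842) × √(2/100) = 0.396 SD to (2.241 + 0.842) × √(2/100) = 0.436 SD. That is a simple two-group approximation with 100 per arm.

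**Aim 2.** State that the plan's existing Bonferroni rule, or Holm, covers the laboratory measures before any of them enters the mediation step, and list the measures in each family. The Assays section names two forms of ghrelin, so the list should say which is tested.

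With a family of five, the smallest p-value must be below 0.01. On the same approximation the detectable difference at that threshold is (2.576 + 0.842) × √(2/100) = 0.483 SD, against 0.396 SD at 0.05. It would be larger in practice because participants may decline the laboratory sessions.

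Both changes are to wording only and should be dated before the treatment codes are opened.

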### **SECTION I: RESEARCH PLAN**

1. **Statement of Purpose:** State the scientific aim(s) of the study, or the hypotheses to be tested.

**PRIMARY AIM 1.** To conduct a double-blind, placebo-controlled parallel group study to evaluate the efficacy of naltrexone HCI and bupropion HCI (NB) versus placebo in patients with binge-eating disorder (BED), stratified by obesity status (n=50 per cell, n=200 total).

- *Hypothesis 1.1.* We hypothesize that NB will be superior to placebo for reducing binge eating among patients with BED.
- Hypothesis 1.2. We hypothesize that NB will be superior to placebo for reducing weight among BED patients with obesity.
- Hypothesis 1.3. We will examine whether BED patients with and without obesity derive differential benefit of NB versus placebo on reducing binge eating (i.e., does obesity moderate outcomes).

**PRIMARY AIM 2.** To evaluate correlates and possible mechanisms underlying the effect of NB on binge eating among all participants (n=50 per cell, N=200 total). To evaluate the effect of NB on hypothalamic melanocortin and brain reward systems, eating behavior will be assessed with an established human laboratory paradigm designed to evaluate the ability to resist eating preferred high-caloric food and subsequent over-eating. We will evaluate potential mechanisms including eating peptides (leptin, ghrelin) involved in both homeostatic and hedonic aspects of eating, as well as food craving, mood, hunger, and control over eating.

Hypothesis 2.1. We hypothesize that potential medication-related changes in eating behavior, eating peptides and craving assessed in the laboratory will mediate clinical outcomes during the 12-week treatment period (i.e., rates of binge eating).

Hypothesis 2.2. We hypothesize that NB versus placebo will increase the ability to resist eating preferred high-calorie food, and will reduce overall calorie consumption in patients with BED.

Hypothesis 2.3. We will examine whether BED patients with and without obesity derive differential benefit of NB versus placebo with regards to their ability to resist eating or calories consumed (i.e., does obesity moderate outcomes).

**EXPLORATORY AIM 3**. To assess eating and drinking behavior, food craving, and mood 'in the field' in a subset of participants (n=60).

2. **Probable Duration of Project:** State the expected duration of the project, including all follow-up and data analysis activities.

September 2017 – September 2024

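### Secondary outcomes: Holm's step-down procedure is a cheap improvement on the planned single-step Bonferroni correction, which is valid but never more powerful

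*Combined protocol and SAP*

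**What the plan says.** Section I, item 13 sets two rules. For the primary outcomes, "Primary outcomes will be tested at the two-sided alpha 0.05 threshold". For the rest, "Secondary analyses will be adjusted for multiple tests using the Bonferroni correction". The plan sets the divisor by "basing the adjustment on the number of conceptually related statistical tests within each hypothesis". The correction is therefore applied family by family, not over all secondary tests at once. It is the single-step form: each test in a family of m is compared with alpha/m. No step-down method is mentioned.

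Under Secondary Aims, part (a), the plan will "Explore effectiveness of NB medication for BED patients with and without obesity on secondary outcomes". The list covers EDE global score, several eating-behaviour instruments (EDE, TFEQ, FCI, PFS), depression, psychosocial functioning, a metabolic group (lipids, HbA1c, blood pressure, heart rate), and remission and relapse.

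The plan does not list the families, does not give a value of m, and does not state a separate family-wise level for secondary tests. The numbered hypotheses in the Statement of Purpose (1.1 to 2.3) do not cover these outcomes, so a rule that counts tests within each hypothesis does not by itself define their families.

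**The concern.** Bonferroni holds every test in the family to alpha/m, however many of the others have already been rejected. Holm orders the p-values and compares the smallest with alpha/m, the next with alpha/(m−1), and so on, stopping at the first failure. Its first step is the Bonferroni threshold and its later steps are more lenient, so it keeps every Bonferroni rejection and may add some. Family-wise error stays at or below alpha under any dependence between the outcomes.

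At stake is efficiency in reading the secondary outcomes, above all in families where several related scales respond together. No error rate is breached, and the primary test lies outside this correction.

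**Working it through.** **Inputs from the documents.** Section I gives "n=50 per cell, n=200 total", so the medication main effect compares 2 × 50 = 100 with 100. Item 12 cites attrition of 20% to 38% in earlier studies; a 35% loss leaves 100 × 0.65 = 65 per arm. There is no power figure in the plan to reproduce.

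**Assumptions.** Standardised effect d = 0.3 to 0.5; family size m = 2, 4 or 8; correlation between test statistics 0 to 0.6; family-wise alpha 0.05 two-sided; a two-group z-test in place of the mixed model.

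**Step 1: power of one test under Bonferroni.** The mean of z is d × √(n/2). For d = 0.4 and n = 100 this is 0.4 × √50 = 2.828. Power ≈ Φ(2.828 − critical value):

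- unadjusted: Φ(2.828 − 1.960) = 80.7%
- m = 2: Φ(2.828 − 2.241) = 72.1%
- m = 4: Φ(2.828 − 2.498) = 63.0%
- m = 8: Φ(2.828 − 2.734) = 53.7%

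Most of the loss comes from adjusting at all (80.7% to 63.0% at m = 4). Holm can recover only part of it.

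**Step 2: Holm by hand for m = 2, independent tests.** Holm rejects a hypothesis if its p ≤ 0.025, or if its p ≤ 0.05 and the other p ≤ 0.025.

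- Both effects real: 0.721 + (0.807 − 0.721) × 0.721 = 78.3%, against 72.1% for Bonferroni, a gain of about 6 points.
- One effect real: the gain is (0.807 − 0.721) × 0.025 = 0.2 points.
- One effect real, chance of falsely rejecting the other: Bonferroni 2.5%; Holm 0.025 + 0.025 × 0.721 = 4.3%. Both are below 5%, but Holm uses more of it.

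**Step 3: larger, correlated families.** Simulation with 200,000 sets of test statistics per setting, d = 0.4, correlation 0.5. Entries are average power per true effect, Bonferroni to Holm.

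| Family | Truly affected | 100 per arm | 65 per arm |
|---|---|---|---|
| m = 2 | 1 | 72.2% to 72.4% | 51.7% to 51.8% |
| m = 2 | 2 | 72.1% to 77.2% | 51.6% to 56.8% |
| m = 4 | 1 | 63.1% to 63.2% | 41.5% to 41.6% |
| m = 4 | 2 | 63.0% to 65.2% | 41.4% to 43.2% |
| m = 4 | 4 | 62.8% to 71.7% | 41.4% to 49.1% |
| m = 8 | 1 | 53.7% to 53.7% | 32.5% to 32.6% |
| m = 8 | 4 | 53.8% to 56.9% | 32.5% to 34.6% |
| m = 8 | 8 | 53.8% to 64.6% | 32.4% to 40.0% |

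A separate run over 65 and 100 per arm, d = 0.3, 0.4 and 0.5, and correlation 0, 0.5 and 0.6 (100,000 sets per setting) gave:

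- one outcome affected: gain 0.0 to 0.3 points;
- half of a family of 4 or 8 affected: 1.8 to 3.3 points at d = 0.4, and 0.6 to 3.5 over all d;
- all affected: 4.9 to 11.9 points at d = 0.4. At the low corner (65 per arm, d = 0.3) the gain is only 1.4 to 4.6; the largest value anywhere was 12.4.

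The chance of at least one true finding differed by no more than about 0.1 point. No simulated trial had a Bonferroni rejection that Holm missed. With m = 1 the two methods are identical.

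**The case against.** The strongest reply is that this is a choice between two valid methods, and that the gain depends on assumptions the documents do not supply. Much of that stands.

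- **Realised error.** A reader might infer that Bonferroni discards real effects for nothing. That does not hold. When some effects are real, its actual false-positive rate is lower: with m = 5, four true effects, d = 0.5, 70 per arm and correlation 0.5, the remaining null is falsely rejected about 1.0% of the time, against 3.1% under Holm. Bonferroni also gives simple matching simultaneous intervals. What is equal is the guaranteed 5% ceiling, and at that ceiling Bonferroni never has more power.
- **Do all outcomes move together?** The documents do not show it. The risk section (item 10) cites a trial in which blood pressure and pulse changed less favourably on NB than on placebo (systolic −0.4 v −2.1; pulse 1.0 v −0.1). A picture in which every secondary outcome benefits by a moderate amount is therefore the best case for Holm.
- **Family size.** If EDE global or depression stands alone as a family, nothing changes for it.
- **Importance.** A reader might infer that the trial's clinical reading rests on these outcomes. The study overview (item 4) names binge-eating frequency as the primary outcome measure, and Secondary Aims is worded as exploratory.
- **Dependence on grouping.** Under Holm, one outcome's result depends on the other p-values in its family, so undefined families matter more. That is a reason to list the families. Bonferroni needs the same list to fix m.

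None of this gives a setting in which Bonferroni is the more powerful method at the same guaranteed level.

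**Conclusion.** This is a cheap improvement and not an error in the plan. Single-step Bonferroni within families is valid; Holm at the same family-wise 5% level is at least as powerful under any dependence. That statement needs no trial assumptions.

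The size of the gain does. It runs from nothing when a single outcome in the family is affected to roughly 12 points per true effect when every member of a large family is, and is lower where effects are small or attrition is high. The effect sizes, family sizes, correlations and the 0.05 level for secondary families are all assumed. The documents do not support a claim that any particular secondary finding would be lost.

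**What to change.** In item 13, name Holm's step-down procedure in place of the Bonferroni correction, for example: *Secondary tests within each pre-listed family are adjusted by Holm's step-down procedure at a two-sided family-wise level of 0.05; Holm-adjusted p-values are reported.*

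In the same edit, list which outcomes, subscales and time points form each family, and fix that list before anyone analysing the data is unblinded. State the family-wise level for secondary tests explicitly.

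Cost: a few lines of text and no new data, visits or participants. If simultaneous confidence intervals are wanted, those that match Holm are harder to build. Bonferroni intervals could be shown beside the Holm p-values, with a note that the two may disagree at the margin.
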